## 5. Study Procedures

Describe and explain the study design, including:

- Procedures to monitor subjects for safety, including who will review the data and at what frequency for safety issues.
- Procedures performed to lessen the probability or magnitude of risks.
- All drugs and devices used in the research and the purpose of their use, and their regulatory approval status.
- The source records that will be used to collect data about subjects. (Attach all surveys, scripts, and data collection forms.)
- What data will be collected including long-term follow-up.
- The duration of an individual subject's participation in the study.
- The duration anticipated to enroll all study subjects.
- The estimated date for the investigators to complete this study (complete primary analyses)

NOTE: It should be clear exactly which procedures will be conducted for the research as opposed to procedures the subjects would undergo (in the exact manner described in the protocol) even if they were not participating in the study.

Describe procedures that will be followed when subjects withdraw from the research, including withdrawal from intervention but continued data collection.

Describe any anticipated circumstances under which subjects could be withdrawn from the research without their consent.

Describe any procedures for orderly termination.

If the study involves genetic testing or collection of genetic information, describe this.

## Data, sources, and date range

The following table shows how outcomes data will be collected

Source (specify) (i.e., from KPWA, or from an existing or previous study)	Key Information/Description of Variables	Date Range
---	--	------------

activPAL activity monitor	PRIMARY OUTCOME 

• Change in mean daily sitting at 6 months

	Baseline to 6-months
ORIGINAL COHORT: In-person measurement visit at KPWHRI  COVID-19 UPDATE AND NEW REMOTE COHORT REMOTE MEASUREMENT	PRIMARY OUTCOME 

• Change in systolic and diastolic blood pressure

	Baseline to 6-months
In-person measurements collected at clinic visit at KPWHRI  COVID-19 UPDATE AND NEW REMOTE COHORT: REMOTE MEASUREMENT OF WEIGHT	SECONDARY OUTCOMES 

• Change in HbA1c (Original Cohort only)

• Change in Weight

	Baseline to 6 months
In-person measurements collected at clinic visit at KPWHRI  COVID-19 UPDATE and REMOTE COHORT: REMOTE MEASUREMENT OF WEIGHT and BP	OTHER EXPLORATORY OUTCOMES for i-STAND BOOSTER ONLY 

• Change in HbA1c (original cohort only)

• Change in Weight

• Change in systolic and diastolic blood pressure

	Baseline to 12 months
activPAL activity monitor	OTHER EXPLORATORY OUTCOMES for i-STAND BOOSTER ONLY 

• Change in time spent sitting or lying down

• Change in step counts

	Baseline to 12 months
Participant questionnaire	OTHER EXPLORATORY OUTCOMES 

• Change in quality of life

• Change in depressive symptoms

	Baseline to 6 months

	
 
• Change in physical function
 
	
VDW	
Various chronic conditions (e.g. diabetes, cardiovascular conditions); lab values for HbA1c, cholesterol; blood pressure; blood pressure medications; height and weight; medical events (e.g. falls, hospitalizations, heart attack, stroke, blood clots); and, healthcare costs.
	
One year prior to first Study Visit date to the end of the study for up to 5 years after the study ends, no later than June 1, 2028

**2022 BUDGET CUT UPDATE:** As of March 31, 2022, neither the i-STAND cohort nor the control cohort will have a 12-month assessment to collect the outcomes listed in the table above. To be as clear as possible - those items have been highlighted in green.

**Sequential description**

(see attached Study Flow Chart)

**ORIGINAL (in-person) COHORT**

1. Subjects are contacted by the KPWA survey research team and provide oral consent over the phone in the initial screening and eligibility process; if eligible and interested, subjects will be mailed an activPAL device along with instructions on how to wear it for one week and will be scheduled for their first/baseline visit at KPHR research clinic.
2. **COVID-19 UPDATE: BASELINE VISITS ARE CURRENTLY ON HOLD** Subjects will attend a baseline screening visit at KPHR research clinic in downtown Seattle.
  - a. At the baseline visit, prior to signing the consent form, the RS will ask the potential participant to recap briefly their understanding of the study. Once subjects have signed written, informed consent at the baseline visit they will have baseline measurements taken, including height, weight, waist circumference, physical function and blood pressure. They will have a small amount of blood collected by finger prick. They will turn in their activPAL device to the research specialist. They will also complete a survey containing self-reported scales regarding health symptoms (depressive symptoms, pain, fatigue), daily activities, and psychosocial mediators (e.g. habit strength, self-efficacy). All participants will receive a \$40 incentive for completing measurements at the baseline visit. If participants inquire about their blood values or blood pressure, we will share the information with them but without interpretation and advise them to see their provider if they have questions or concerns.
  - b. After baseline activPALs are returned, participants will be randomized (using a link created by the study biostatistician and programmer) to receive i-STAND (N = 142) or healthy lifestyle control (N = 142). To ensure that baseline sitting time is balanced, we will stratify participants into two groups based on self-reported sitting-time using median sitting time from our pilot work as a cut point: moderate (<8.5 hours/day) and high ( $\geq 8.5$  hours/day). We will also stratify by obesity level (30-35 vs 35+kg/m^2) and

blood pressure (systolic BP over or under 130).

- c. After completing measurements, participants randomized to receive the i-STAND intervention condition will meet with a health coach and have an in-person coaching session (at Baseline Visit). During the first intervention session they will review a feedback chart depicting their daily sitting time, standing time, and breaks from sitting from the activPAL they wore for baseline. In the case that the coach encounters difficulty with the STATA software that creates the feedback chart output, coaches will use the raw activPAL data (does not take sleep hours out of the download) and share this with participants. They will explain the data in the same way they would if they were able to produce a feedback chart. Participants in the i-STAND cohort will receive the i-STAND study workbook, self-monitoring forms, and offered a wrist-worn prompting device (Fitness activity band), and a portable tabletop standing podium/desk to be used at home or work or wherever the participant chooses to use it (see i-STAND Workbook for photos and instructions for both items) to cue breaks from sitting. The health coach will provide background information on how sitting could impact their health. The coach will review the feedback chart with the participant, provide reinforcement for times during the week when the participant took more breaks from sitting, assess and enhance participant motivation and uncover values (using motivational interviewing principles) to inform developing an action plan to meet graded goals based on participant values. The action plan will include target goals, when/how/where tasks will be performed, strategies to overcome barriers, and how goals map to participant values. Discussion will cover principles of habit formation. The health coach will model taking breaks from sitting by inviting the participant to stand with them at least once during the session.
  - During the in-person session, participants will be instructed in using the wrist-worn activity band and standing desk to help remind them to take breaks from sitting. Our pilot work strongly supported the need for these cues. The band subtly vibrates to prompt a break at preselected intervals (ex: 15, 30 or 60 minutes) and will be set to prompt every 15 minutes to remind them regularly to take breaks from sitting. Because many older adults don't feel comfortable setting up technology and mobile tools, the device will be preset so it functions without syncing to another device. Participants who want to use the activity band smartphone application will receive additional instruction. Study staff will not have access to any data from the device. If any participants feel the frequency (every 15 minutes) is too much, study staff can re-set the band at a lower frequency based on the participants' preference.
  - Those who express interest in other features of the Fitness wrist band will be given a handout showing how to program the device to track other things (ex: steps taken, calories burned), however the study does not track on any of these features/options and the coach will remind the participant that the study is solely interested in whether they find the vibration reminders useful as an outward reminder to stand. (*Usefulness will be measured in a 3-month survey (see section 3a next page).*
- d. Participants in the Healthy Lifestyle Control group will meet with a health coach and have an in-person coaching session where they will review the Healthy Living

materials and choose topics of interest to focus on throughout the program. They will learn about how to set clear, actionable goals. They will receive a Healthy Living workbook. The health coach will provide background information and help the participant choose topics of focus to inform developing an action plan to meet graded goals based on participant values. The action plan will include target goals, when/how/where tasks will be performed, strategies to overcome barriers, and how goals map to participant values.

- e. All participants will be asked by the health coach during the baseline visit to provide additional contact information. This will be collected on a separate sheet and will be entered into the ACCESS database used by the team.
3. After the initial in-person session:
  - a. All i-STAND participants will receive one more in-person session and 8 follow-up phone calls (10 contacts total) from their health coach over 6 months. All participants will also be sent an activPAL to wear, as well as a survey, at the mid-point (Month 3) and will receive a \$20 incentive for wearing the activPAL at month 3. All participants will receive a reminder phone call from the RS to confirm receipt of the packet containing the activPAL and the survey. If the packet was not received, the RS will resend another packet. At the 3-month mark, health coaches will also collect satisfaction data on use of the devices. This information will be collected over the phone and input into REDCap by the coaches, so as to avoid contaminating the survey data collected by the blinded research specialists, who will be managing the primary survey distribution and data collection.
  - b. All Healthy Lifestyle Control Participants will receive 9 follow-up phone sessions after their initial in-person session (10 contacts total). Each call will cover a topic of interest to the participant (see Table 4). Relevant content from the Healthy Living workbook will be briefly reviewed and goals will be set. Follow-up calls will check-in with prior calls. The calls will occur every 2-3 weeks over the first 6 months of the study.
  - c. COVID-19 UPDATE: both i-STAND and Health Lifestyle participants will be offered, using an Addendum to Consent oral agreement, the option of additional coaching calls beyond the 10 sessions to occur on a monthly basis. See page 15 of this protocol for details and see the Addendum Consent for script. 3-month assessments will also still be mailed. A study RS will assemble packets with charged activPALs and participant surveys at their home and mail to participants via the USPS. Study RS has sanitation procedures that are used at the office that will also be used at home in assembling packets (gloved, wipes, etc). Participants will mail the packets back to KPWHRI and a study RS will be checking our mailbox once a week for returned devices/surveys.
  - d. All participants (i-STAND and Healthy Lifestyles control group) will attend a 6-month measurement visit. A few weeks prior to the visit and to mailing the activPAL device to the participants, the RS will call the participant to ensure we have accurate contact information and to remind them of the upcoming timepoint. If the participant has

requested that scheduling visits/reminders of visits be done via email, this information will be sent via email from the RS. The same measurements and assessments will be taken as at baseline except a study satisfaction questionnaire will be included in the self-reported survey. All participants will receive a \$40 incentive for completing measurements at the 6 month visit. For those participants who do not show up to their scheduled 6-month visit, we will attempt to reach them by phone and then by mail, encourage their participation and completion of this timepoint. At this in-person visit, if participants inquire about their blood values or blood pressure, we will share the information with them but without interpretation and advise them to see their provider if they have questions or concerns. After completing the 6-month measurement visit, all I-STAND participants will be re-randomized to EITHER receive i-STAND booster sessions (5 additional phone contacts) or no further intervention for 6 months. The health coach will call each participant after they complete their 6 month measurements to inform them of their assignment.

- COVID-19 UPDATE: We will be ordering and sending directly to individual participants from a third party vendor (pending oral consent from participants) Omron BP Monitors (The Omron 3-Series BP7100 model) for any 6 and 12-month measurements. Participants will not be expected to return this device. Instructions will be included in the mailed packet that also includes the survey, activPAL, paper measuring tape (Medline 72" paper measuring tape). RS staff will call participants to conduct the chair-sit measurement and to verbally collect the BP/weight/waist measurements from participants. As usual, study packets mailed to participants will include return envelopes for the activPALs and the surveys.
- We will send incentives to participants when business returns to normal and we are able to send cash incentives. Participants will be notified that they will receive their incentives at a later time.
- We have amended Supplement B to request permission to use email to send the link for the survey (REDCap) to participants for whom we have email addresses and who have given us permission to contact them using email.
- We will track those participants who receive a device from a third party vendor on the internal PHI Disclosure Tracking Form (<https://ghriweb01.ghc.org/disclosuretrack/seldisc1.aspx>)

- e. For those re-randomized into the i-STAND group, 5 booster calls spread over 6 months (about every 6 weeks) will focus on maintaining improvements (or continuing to improve for those who have not met goals), action planning, problem-solving, preventing relapse, and continuing to use previously learned skills and tools.
- f. Participants in the i-STAND booster arm will wear the activPAL for an interim week between measurement visits (i.e., at 9 months) and receive an additional feedback chart to help monitor progress towards goals.

COVID-19 UPDATE: Until we return to normal business, this intervention activPAL wear has been temporarily suspended.

- g. Participants in the i-STAND booster arm will receive a supplemental survey at 9-month mark to gauge their use of the tools – the standing desk and the Fitness wrist-band.
- COVID-19 UPDATE:** Until we return to normal business, this intervention survey has been temporarily suspended.
4. All participants (i-STAND and healthy living control group) will attend a final, 12-month measurement visit. Prior to the visit they will be mailed an activPAL to wear for a week. The same measurements will be taken as at baseline and at the 6-month visit, including a survey. All participants will receive a \$40 incentive for completing measurements at the 12 month visit. i-STAND cohort participants will be allowed to keep their wrist bands and standing desks. Once again, at this in-person visit, if participants inquire about their blood values or blood pressure, we will share the information with them but without interpretation and advise them to see their provider if they have questions or concerns.
- COVID-19 Update – see 3c. above for details**
5. Shortly after completing the active, 6-month phase of the study, participants will receive a call asking for their oral consent to an interview. After completing the full year in the study including the final, 12-month visit, they will receive a letter thanking them for their participation and inviting them to participate in a final exit interview in the coming months. The letter will provide an opt-out if they do not want to do an exit interview. If we do not hear from the participant, we will assume they are open to receiving an exit interview phone call.).

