COVID-19 UPDATE: We have created an Addendum to Consent oral script to offer participants the option to continue coaching past the protocol timepoint as dictated in the original consent form until they are able to complete their remote 6 or 12 month assessments (for those receiving the booster intervention). The majority of participants will only have 10 coaching sessions and a subsection of i-STAND cohort will receive booster sessions. This is to ensure that participants are still working on their study goals up until their outcome measures can be assessed. For those who have already completed a 10th call, the coach will reach out by phone and ask if they are interested in optional additional coaching. If the participant is interested, the coach will use the oral consent process. For those who have not yet had this 10th session and have one forthcoming, the coach will ask at the end of that call if they are interested in optional additional coaching and use the oral consent process.

COVID-19 UPDATE: We have created an Addendum to Consent oral script to offer participants the option of receiving a blood pressure monitor (to keep) which we will send by a third party vendor. The oral consent is to verify their permission to share their mailing address and name with a third party in order to mail the device. Participants can choose not to allow this, in which case we will not collect their blood pressure data in the remote measurement visit.

REMOTE (phone) COHORT

No addendum consents will be implemented at this time with any newly recruited participants into the Remote Cohort. The additional coaching option will not apply to this cohort and the consent to give their name/address to a third party is covered in the screening that occurs during recruitment by the survey research group.

2022 BUDGET CUT UPDATE:

As of March 31, 2022, and upon approval of this IRB submission (Package 58) we will be mailing an Informational Letter to participants in both cohorts advising them of the change to the study and providing them a phone number to call if they have concerns. These letters will be sent in lieu of a revised consent form. In the letter we will highlight:

- Removing the 12-month visit which means \$30 less than they originally thought they'd receive for participation
- There is no change to risk
- There will be no potential for additional coaching beyond 6-months (only offered to a subset of the participant population)

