- f. All participants will be asked by the health coach during the baseline visit to provide additional contact information. This will be collected on a separate sheet and will be entered into the ACCESS database used by the team.
5. After the initial baseline phone coaching session:
  - a. All i-STAND participants will receive 9 follow-up phone calls (10 contacts total) from their health coach over 6 months. An optional activPAL wear for i-STAND participants will take place at the 6-week mark, after which their data will be reviewed on a subsequent coaching call.
  - 2022 BUDGET CUT UPDATE: As of March 31, 2022, we are no longer offering the optional 6-week wear as a part of our staff time adjustments
  - b. All Healthy Lifestyle Control Participants will receive 9 follow-up phone sessions after their initial baseline phone coaching session (10 contacts total). Each call will cover a topic from the workbook (see Table 4). Relevant content from the Healthy Living workbook will be briefly reviewed and goals will be set. Follow-up calls will check-in with prior calls. The calls will occur every 2-3 weeks over the first 6 months of the study.
  - c. All study participants will be sent an activPAL to wear, as well as a survey, at the mid-point (Month 3) and will participate in a 3-month measurement visit by phone with a research specialist, repeating the measurements and instructions from the baseline visit. If the participant has requested that scheduling visits/reminders of visits be done via email, this information will be sent via email from the RS. They will receive by mail a \$30 incentive for completing the 3-month visit. All participants will receive a reminder phone call from the RS to confirm receipt of the packet containing the activPAL and the survey. If the packet was not received, the RS will resend another packet. At the 3-month mark, health coaches will also collect satisfaction data from the i-STAND group on their use of the devices. This information will be collected over the phone and input into REDCap by the coaches, so as to avoid contaminating the survey data collected by the blinded research specialists, who will be managing the primary survey distribution and data collection.

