**Attention Control group:**  
ORIGINAL (in-person) COHORT:

This intervention was designed to control for a similar amount of contact time and attention, nonspecific treatment effects, study satisfaction, and patient expectations. Attention controls have been used in previous physical activity intervention trials among older adults for whom time, attention, and social support may be particularly salient factors that affect study outcomes. Attention control participants will receive the same number of contacts as i-STAND participants and a study workbook with general healthy living content based on the usual care available to KP members. During the initial in-person session, participants will choose up to 9 topics from a list of 17 to review with their health coach during subsequent sessions (see Table 2). The content provided will not include any information that could impact sitting time or physical activity. During the 9 follow-up calls, the health coach will review progress towards prior goals, engage participants in brief discussions of the session topic, and set goals for new topics. All health-related content included in the workbook and delivered by the health coach is currently available online to KP members and is reviewed and updated regularly by KP physicians. The attention control group will receive no further intervention after the 6-month measurement visit.

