**Aim 1: Determine the efficacy of i-STAND to improve primary and secondary outcomes at 6 months.**

*Primary Outcome Analysis:* Our primary outcomes are change from baseline in mean daily sitting time and systolic and diastolic blood pressure (described in Section C12). We will compare group means for our primary outcomes between participants randomized to i-STAND versus attention control using linear regression with generalized estimating equations (GEEs) including both outcome time points at 3 and 6 months. GEE is used to account for multiple outcomes measured on the same study participant along with relaxing the normality assumption that standard linear regression methods require. We will adjust for baseline covariates including participant age, sex, physical function, and respective baseline outcomes with other covariates that are imbalanced in preliminary analyses. If dropout is above 15%, we will employ imputation techniques to address missing data issues. However, our focus will be on minimizing dropout rates. Analyses for secondary outcomes including lipids, fasting glucose, weight, and waist circumference will be similar, adjusting for respective baseline outcomes in the analysis. *Aim 2: Determine the maintenance of sitting and blood pressure reductions over 12 months.* We will conduct a sequential series of analyses using a similar statistical framework as outlined for Aim 1, but using 12-month follow-up data. We will first run a regression model with three groups (attention control, i-STAND no boosters, and i-STAND with boosters) including baseline covariates as outlined above. We will then

assess differences in primary outcomes at 12 months in the two i-STAND groups: with and without the booster intervention. If a significant difference in a given primary outcome is found in sitting time at 12 months between the i-STAND booster versus no booster groups (Scenario 1), we will further compare the i-STAND booster and no booster groups to the attention control group. Scenario 1 assessments will determine if i-STAND with boosters is better than i-STAND without boosters and if either or both I-STAND groups are better than attention control at 12 months.

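### The Original cohort matches the arms on number of coaching contacts but not on mode, and the pooled Aim 1 model names no cohort term although delivery and measurement differ by cohort

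*Combined protocol and SAP*

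**What the plan says.** Section 5, Original (in-person) cohort. Item 2c says that i-STAND participants "will meet with a health coach and have an in-person coaching session (at Baseline Visit". Item 3a continues: "All i-STAND participants will receive one more in-person session and 8 follow-up phone calls (10 contacts total". Item 3b gives the comparator: "All Healthy Lifestyle Control Participants will receive 9 follow-up phone sessions after their initial in-person session (10 contacts total". Item 3c adds optional monthly coaching beyond the ten contacts, offered to both arms because of COVID-19.

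Section 5, Remote (phone) cohort. After a first phone session, item 5a says "All i-STAND participants will receive 9 follow-up phone calls (10 contacts total", and item 5b gives control the same pattern. Section 4.o says of this cohort: "The additional coaching option will not apply to this cohort".

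Section 5, Attention Control group, states the aim, "This intervention was designed to control for a similar amount of contact time and attention", and the commitment that serves it, "Attention control participants will receive the same number of contacts as i-STAND participants". No session length is given for either arm.

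Section 5.a, Aim 1, pools the cohorts: "We will compare group means for our primary outcomes between participants randomized to i-STAND versus attention control". The named covariates are age, sex, physical function and the baseline outcome, plus any covariate found imbalanced. Randomisation (Original item 2b, Remote item 4b) is stratified by self-reported sitting time, obesity level and systolic blood pressure. Section 5.a opens with a promise of secondary analyses for COVID-19 changes in both cohorts and does not describe them.

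**The concern.** An attention control is there so that a difference between arms can be credited to the sitting-reduction content and not to time spent with a coach. In the Original cohort i-STAND has one more face-to-face session than control; in the Remote cohort neither arm has any. The single Aim 1 estimate therefore averages two versions of the contrast.

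The cohorts also differ in how a primary outcome and a model covariate are obtained. Differences of that kind shift outcomes in both arms alike and add variance unless the model accounts for cohort. Because no cohort analysis is specified, any cohort-specific result would be chosen after the event under an open-ended promise. At stake are some precision and a clear statement of what the pooled average represents.

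**Working it through.** **Step 1. Planned coaching contacts by arm and cohort** (Section 5, Original items 2c, 2d, 3a, 3b; Remote items 4d, 4e, 5a, 5b).

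| Cohort | Arm | In person | Phone | Total |
|---|---|---|---|---|
| Original (100) | i-STAND | 1 + 1 = 2 | 8 | 10 |
| Original (100) | Control | 1 | 9 | 10 |
| Remote (184) | i-STAND | 0 | 10 | 10 |
| Remote (184) | Control | 0 | 10 | 10 |

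The count is equal everywhere. The mode differs by one contact in ten, in 100/284 = 35.2% of the sample.

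**Step 2. Other differences between cohorts** (assessment descriptions for each cohort in Section 5).

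- Blood pressure: Original baseline is taken in clinic on one monitor, and follow-up during the COVID-19 period on a mailed home monitor of another model. Remote uses the mailed home monitor throughout.
- Blood pressure at 3 months: Remote repeats the baseline measurements at a phone visit (item 5c). Original has only a mailed activPAL and survey (item 3a).
- Physical function, a named covariate: the full performance battery in Original (chair rise only during remote visits), the chair-rise component only in Remote.
- Control topics: chosen by the participant in Original; the first five assigned in Remote.
- Extra coaching: Original only, both arms.

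**Step 3. Reproduce the planned sample size** (Section 5.a, Power calculations: difference 41 min/day, SD 97, power 90%, loss 15%). Alpha is not stated; two-sided 0.05 is assumed.

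- n per arm = 2 × (97/41)² × (1.960 + 1.282)² ≈ 118, so 236 in total; 236/0.85 ≈ 278, against the stated 284.
- Observed: 284 × 0.85 = 241. Power at 120.5 per arm: SE = 97 × √(2/120.5) = 12.5; 41/12.5 − 1.96 = 1.32, giving 90.7%.

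The pooled calculation is sound.

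**Step 4. What a cohort covariate costs and gains.**

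- Cost: one degree of freedom. The t critical value moves from 1.9699 (239 df) to 1.9700 (238 df).
- Gain: if mean change differs by δ between cohorts in both arms, leaving cohort out adds p(1 − p)δ² to the outcome variance, with p = 0.352 and p(1 − p) = 0.228. The documents give no δ. As a yardstick, take δ equal to the planned detectable difference and treat the planning SD as within-cohort. Systolic pressure: 0.228 × 6.2² = 8.8 against 14.7² = 216, or 4.1%. Sitting: 0.228 × 41² = 383 against 97² = 9409, also 4.1%. The standard error rises by √1.041 = 1.02, about 2%.

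**Step 5. How precise cohort-specific effects would be** (assumed: SD 97 and 15% loss in each cohort, 1:1 within cohort).

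| Quantity | Original | Remote |
|---|---|---|
| Observed (per arm) | 85 (42.5) | 156.4 (78.2) |
| SE = 97 × √(2/n) | 21.0 | 15.5 |
| 95% CI half-width, min/day | 41 | 30 |
| Power for 41 min/day | about 49% | about 75% |

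Arm-by-cohort difference: SE = 97 × √(2/42.5 + 2/78.2) = 26.1. Half-width = 1.96 × 26.1 = 51 min/day. The difference detectable with 90% power is 3.24 × 26.1 ≈ 85 min/day.

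**The case against.** The plan promises the same number of contacts and delivers 10 against 10. Items 3a and 3b disclose the mode openly. Participants are randomised within each cohort, so pooling does not in itself bias the comparison. The rule on imbalanced covariates could bring cohort in, COVID-19 survey variables are to be examined as moderators, and COVID-19 secondary analyses are promised. A cohort covariate cannot remove a two-against-one difference that lies inside one cohort. The cohorts also differ in calendar period, catchment area and home measurement, so comparing them cannot isolate one in-person session.

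Most of this stands and limits the point. It does not close the gap: the imbalance rule acts only if the arms happen to differ on cohort, the moderators are survey items, and the secondary analyses have no content.

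A reader might go further in four ways that the documents do not support.

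- That attention matching fails. Without session minutes, unequal contact time cannot be inferred.
- That the extra session inflates the pooled sitting effect by a stated amount. The documents give no effect for an in-person session, so no figure can be defended.
- That the Remote cohort is a clean attention-matched comparison. Remote i-STAND participants had an optional extra activPAL week at 6 weeks, reviewed on a coaching call, until March 31, 2022 (item 5a); control had none.
- That extra coaching is an imbalance by design, or that values taken after it should be excluded. It was offered to both arms. Uptake is a choice made after randomisation, so an analysis that drops those values is not evidence on the treatment effect.

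**Conclusion.** The point holds as one of specification and interpretation, not of bias. In 35% of the planned sample the arms match on number of contacts but differ by one in-person session. Delivery, blood pressure measurement and the physical-function covariate vary by cohort, and the Aim 1 model names no cohort term. The pooled comparison of the two packages as delivered remains valid.

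The precision at stake is modest: about 2% of the standard error if the cohorts' mean changes differ by as much as the planned detectable difference, less if they differ by less. The larger gain is a result that can be read, with cohort-specific estimates fixed in advance. Those estimates stay descriptive, because the arm-by-cohort interval of about ±51 minutes is wider than the 41-minute target. These figures assume SD 97, 15% loss and 1:1 allocation in each cohort, and two-sided alpha of 0.05.

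**What to change.** - Section 5.a, Aim 1: add cohort (Original/Remote) as a covariate in every Aim 1 model, and say which physical-function score is entered, since only the chair rise is common to both cohorts.
- Section 5.a, opening paragraph: define the COVID-19 secondary analyses to include the treatment effect within each cohort and the arm-by-cohort difference, with confidence intervals, reported descriptively.
- Reporting: tabulate in-person and phone contacts actually delivered, and uptake of extra coaching, by arm and cohort.
- Section 5, Attention Control group, Original cohort: state that matching is on number of contacts, with one more in-person session for i-STAND.

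Cost: protocol wording and a few extra model runs. Cohort is known for every participant and completion of sessions and calls is already tracked. The sample size stays at 284. The downside is that readers may over-read imprecise cohort estimates, so the text should say that they cannot isolate the effect of one in-person session.
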